3.2 Hypotheses and tests

We first propose hypotheses regarding relationships between CVD beliefs, information and behaviour that will be tested using data on elicited beliefs and the information experiment, which are summarized in Table 1.

Q1: Are the elicited beliefs interpretable as subjective probabilities?

[H1a] Elicited probabilities have face validity and are consistent with rules of probability.

Tests:

- Use data from section A.
- Face validity: Ask for perceived life expectancy and for perceived chance of living past 80 years. Check whether those variables are positively correlated.
- Monotonicity: Ask for perceived probability of a destructive earthquake in respondent's province within one year and within 10 years and check percentage of respondents for whom the latter reported probability is not smaller than the former.
- Binary complementarity: Ask for perceived probability that there will be a destructive earthquake in respondents' province within the next 10 years and perceived probability that there will NOT be a destructive earthquake during the same period. Check percentage of respondents for whom the probabilities add up to 1. Compute mean sum of those two subjective probabilities and test whether it equals 1.

[H1b] The prevalence of consistency violations varies with education.

Test:

• Regress binary outcome indicating violation of probability rule (monotonicity and binary complementarity) on education level (and possibly other characteristics).

1 au	ie i Overview of fisk perceptions survey module				
Sect	ion	Treatment group	p Control group		
A.	Training questions	A_{T}	A _C		
B.	Perceived average CVD risk (base rate)	B_{T}	B_{C}		
C.	Information on average CVD risk	C_{T}			
D.	Perceived personal CVD risk (prior)	D_{T}	D_{C}		
E.	Information on personal CVD risk	E _T			
F.	Perceived personal CVD risk (posterior)	F _T			
G.	Information on CVD risk if reduce risk factor exposure	G _T			
Н.	Perceived personal CVD risk if reduce risk factor exposure	H_{T}	H_{C}		

Table 1 Overview of risk perceptions survey module

Note: CVD risk is the probability of having a heart attack or stroke within the next 10 years. We also ask about the probability of getting diabetes within the next 10 years. Sections B, D & F also ask about perceptions of life expectancy and probability of survival to 80.

Q2: Do elicited beliefs incorporate information about objective risks?

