[H2a] Perceived CVD and diabetes risks, perceived life expectancies and subjective survival probabilities are correlated with objective risks predicted from risk factors, including demographics, BMI etc.

Test:

- Regress perceived personal risks from both information treatment group and control group on 10year CVD risk predicted from Globorisk, 10-year diabetes risk predicted from Finnish Diabetes Risk Score (FINDRISC) (Lindstrom and Tuomilehto 2003) and lifetable survival probabilities.³
- Data from section D prior to treatment group receiving information on personal CVD risk.

[H2b] Perceived CVD and diabetes risks, and perceived life expectancies, deviate from predicted risks due to differential weighting of risk factors.

Test:

- Regress perceived personal risks of both information treatment group and control group (section D) on risk factors and compare coefficients with those obtained from regression of predicted probabilities on risk factors. For example, for personal 10-year CVD risk, compare coefficients from model of reported probability to those used in Globorisk risk prediction tool to produce predicted probabilities. Moreover, compare other coefficients to those found in previous literature on the determinants of CVD and diabetes risks, and on life expectancies, such as, family history and exercise.
- Regress perceived personal CVD and diabetes risks, life expectancies and subjective survival probabilities (section D) on the respective perceived base rates (section B) and on risk factors to test the extent to which perceived personal risks are based on perceived base rates with an adjustment to make use of information available to the respondent on risk factors.

[H2c] Perceived base rates for CVD, diabetes, life expectancy and survival probability are higher than objective (predicted) base rates.

Tests:

- Compute mean deviations of perceived base rates (section B) from predicted base rates. A positive (negative) mean deviation hints at overestimation (underestimation) of CVD prevalence/diabetes prevalence/life expectancy/survival probability.
- Compute mean ratios of perceived base rates to objective (predicted) base rates. A mean ratio > 1 (< 1) hints at overestimation (underestimation) of CVD prevalence/diabetes prevalence/life expectancy/survival probability.
- Compare proportion of sample with perceived base rate < objective (predicted) base rate with proportion with perceived base rate > objective base rate.

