- The regression model described in the preceding paragraph is possibly incorrectly specified. It supposes that an individual chooses her health behaviour in response to her perceived level of CVD risk. Logically, behaviour is determined by perceptions of how CVD risk varies with that behaviour. To test this model of rational behaviour, in the regressions described in the previous paragraph, we will replace the perception of personal CVD risk with the difference between this and the perception of what the CVD risk would be if the individual were to reduce her modifiable risk factors. This difference in risk perceptions will be instrumented by regressing it on the treatment group indicator.

Q5: Does the demand for preventive care and health behavior, and ultimately CVD risk, respond to information on current CVD risk?

[H5a] Receiving information on the predicted 10-year CVD risk (including information on the base rate and the risk conditional on reduced exposure to risk factors) affects the demand for primary prevention and lifestyles related to CVD risk. As a result, the provision of information reduces CVD risk.

Test:

- Repeat the regressions described in [H4a] but replace the perceived risk with I_i indicating whether the individual was in the information treatment group. That is, estimate the reduced form effect of the information intervention on behaviour.
- Run the same sort of regression but with the dependent variable being predicted CVD risk at follow-up and conditioning on predicted CVD risk at baseline. If the information intervention has

succeeded in reducing risk factors (blood pressure, smoking and BMI) either through utilization of preventive care or directly through lifestyles, then the mean CVD risk score of the information treatment group will fall relative to that of the control group.

[H5b] Receipt of information on CVD risks affects behaviour not only through the correction of biased beliefs but also by reducing intrinsic uncertainty and increasing confidence in beliefs.

Elaboration

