Individuals may be apprehensive of utilizing their beliefs about CVD risk because they lack confidence in the accuracy of those beliefs. Their beliefs are ambiguous. If individuals are ambiguity seeking in the loss domain, which is often found (Dimmock et al 2015), and are informed that their risks are lower than they had reported, then on gaining confidence in their downwardly revised beliefs they may become responsive to them. Being surer that the CVD risk is 15% rather than being very uncertain that it is 20% may cause an individual to adopt healthier behaviour.

Test:

• Repeat the regressions of the previous test but rather than including a single indicator of treatment group enter two indicators. One identifies respondents in the treatment group informed that their risk is above their initially reported risk. The other identifies respondents in the treatment group informed that their risk is at or below their reported risk. If it is only the correction of bias in risk perceptions that affects behaviour, then only the first group should adopt healthier behaviour. The second group, if anything, should adopt less healthy behaviour. If, to the contrary, the second group responds to the positive news they are given of their CVD risk by adopting healthier habits, this suggests an effect through reduced ambiguity. In addition, we will examine how the provision of information affects stated confidence in individuals' estimates of their risks of heart attack/stroke.

Q6: Is PhilPEN effective in delivering primary prevention of CVD to those who seek care at RHU/CHCs?

[H6a] As currently implemented, PhilPEN does not reduce the risk factor exposure and increase the medication of individuals with elevated CVD risk.

Test:

- Induce random variation in presentation for checkup at RHU/CHCs, which under PhilPEN are required to conduct CVD risk assessment of all patients, to screen those meeting specified criterion, to counsel all those screened on smoking cessation and to provide hypertension and diabetes medication to those at high risk defined by the WHO PEN protocol.
- The information intervention will not be used to generate this random variation since beliefs about CVD risk can impact on behaviour directly even without contact with health facilities and the PhilPEN program.

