5.2 Information on CVD risk

Information provided

Respondents randomly allocated to this treatment group will receive information on the predicted probability of having a heart attack or stroke within 10 years. The predictions will be obtained from the Globorisk tool (Ueda et al 2017). The reasons for using this algorithm are given in the next sub-section. All information will be provided within the risk perceptions module of the survey. Only this module will differ across the two treatment groups (information and lottery) and the control group. Information obtained from earlier modules will be retrieved automatically and used to make predictions of CVD risk consistent with the risk factor profile of the respondent in the information treatment group.

Three types of information on CVD risks will be provided to those in the respective treatment group: a CVD base rate, a personalized CVD risk and an optimal CVD risk. The CVD base rate will be predicted from the respondent's age and sex only. This information will be provided immediately after the respondents are asked to report the chance of someone of their age and gender having a heart attack or a stroke within ten years, and immediately before being asked to report the chance that they will have a heart attack or stroke within that period. The respondents will be presented with the information both as a chance of X in 100 and as the number of people (X) out of 100 the same age and sex as the respondent that doctors would expect to have a heart attack or stroke within ten years.

After reporting their own chance of having a heart attack or stroke within ten years, the respondents in the treatment group will be told the risk for someone with the same age, sex, smoking status, BMI and blood pressure as them. Each respondent will not be told that this is their own chance of having a heart attack or stroke. Rather, if the respondent is female, she will be told that out of 100 women her age, with the same

weight and blood pressure as her, and who (don't) smoke like her, doctors would expect X to have a heart attack or stroke within 10 years. Analogous information will be provided to male respondents. After being given this information, the respondent is asked again to report their 10-year CVD risk. This is interpreted as the posterior belief (after the provision of personalized information).

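### H5b sorts informed respondents by news measured after the base rate was disclosed, but its coefficients measure the whole information package, so the sorting can disagree with the net direction of the news

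*Combined protocol and SAP*

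**What the plan says.** Section 3.2, [H5b], repeats the [H5a] regressions with two treatment indicators in place of one. For the first, "One identifies respondents in the treatment group informed that their risk is above their initially reported risk". For the second, "The other identifies respondents in the treatment group informed that their risk is at or below their reported risk". The plan reads the result as follows: "If it is only the correction of bias in risk perceptions that affects behaviour, then only the first group should adopt healthier behaviour". If the second group becomes healthier instead, "this suggests an effect through reduced ambiguity". The plan also says it will look at stated confidence.

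The effect being split is that of the full package. [H5a] describes it as "including information on the base rate and the risk conditional on reduced exposure to risk factors", set against a control group that receives none of this.

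On timing, Section 5.2 says the base rate is told "immediately before being asked to report the chance that they will have a heart attack or stroke within that period". Table 1 shows the same order: base-rate belief (B), base rate told (C), own risk (D), personal prediction told (E), own risk again (F), then the achievable risk told (G). On the direction of error, [H2c] expects: "Perceived base rates for CVD, diabetes, life expectancy and survival probability are higher than objective (predicted) base rates".

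**The concern.** The starting belief in H5b can only be the information arm's section D answer, D_T. Section B asks about other people of the same age and sex, and no earlier own-risk report exists. D_T already contains the respondent's reaction to the base rate. The plan accepts this elsewhere: the table of dependent variables under [H3a] uses D_T against D_C as the effect of base-rate information.

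So people are sorted on the last step of the news, while each coefficient reflects the whole path from uninformed belief to final belief. The two can have opposite signs. If they do, the *above* group contains people whose belief was lowered overall, and the *at-or-below* group contains people whose belief was raised. What is at stake is the reading that separates bias correction from reduced ambiguity. The size of the package effect in [H5a] is not affected.

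**Working it through.** **1. When the sorting fails.** Let U be the own-risk belief before any information (not collected in the information arm), B the perceived base rate, C the told base rate, D the section D answer and P the told personal risk. H5b sorts on P − D; the net news is P − U. They disagree exactly when P lies between U and D:
- D < P ≤ U: sorted *above*, net news not bad.
- U < P ≤ D: sorted *at-or-below*, net news bad.

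Write D = U + w(C − B), where w is the uptake of the base-rate news. If w = 0, then D = U and there is no disagreement. The documents give no value for w.

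**2. Two worked cases** (assumed values in per cent, w = 0.5, final belief F = D + 0.5(P − D)):
- U = 15, B = 10, C = 20, P = 18. D = 15 + 0.5 × 10 = 20. Since 18 < 20, the person is *at-or-below*. Net news is 18 − 15 = +3; F = 19, a rise of 4. Healthier behaviour here is bias correction, but H5b would read it as ambiguity.
- U = 20, B = 30, C = 12, P = 15. D = 20 − 0.5 × 18 = 11. Since 15 > 11, the person is *above*. Net news is 15 − 20 = −5; F = 13, a fall of 7.

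At w = 0.25 both people are sorted correctly (D = 17.5 and 15.5).

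**3. How often, under assumed beliefs.** Same equations, no ambiguity channel. Risks are scaled to the 11.35% mean in Section 10.1; the base-rate error has SD 10 points and the own-belief noise SD 5 or 10 points (ranges below cover both).

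| Mean error in perceived base rate | w | Net bad news in *at-or-below* | Net good news in *above* | Mean belief change, *at-or-below* | Mean belief change, *above* |
|---|---|---|---|---|---|
| −6 points | 0.5 | 20–22% | 4–5% | −3.2 | +5.5 to +5.7 |
| −6 | 0.75 | 36–46% | 8–10% | −1.1 to −0.3 | +5.7 to +6.0 |
| −6 | 1 | 53–69% | 13–19% | +2.0 to +3.8 | +4.5 to +5.4 |
| +6 | 0.5 | 4% | 21–23% | −9.3 to −8.5 | +2.0 |
| +6 | 0.75 | 8–10% | 32–40% | −9.9 to −9.2 | −0.4 to +0.1 |
| +6 | 1 | 16–23% | 43–56% | −9.1 to −7.0 | −4.3 to −2.5 |
| +15 | 0.5 | 1% | 44–47% | −14.3 to −13.0 | −1.6 to −1.0 |
| +15 | 1 | 3–5% | 71–83% | −18.6 to −16.5 | −12.6 to −10.1 |

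A second model with proportional errors gives the same pattern. Base rates run from 3 to 30% with mean 11.35%; personal risk is base rate × lognormal (log-SD 0.35); perceived base rate is lognormal (log-SD 0.8); own belief is perceived base rate × lognormal (log-SD 0.4); C replaces a share w of B.
- Perceived base rates averaging 20–30%: net good news in *above* is 5–7% at w = 0.25, 13–19% at 0.5, 25–36% at 0.75 and 48–63% at 1. If perceived rates also track the true ones, the range is up to 21% at 0.5 and from 42% at 1. Net bad news in *at-or-below* is 2–3%, 4–7% and 12–22% at w = 0.25, 0.5 and 1.
- Averaging 6%: net bad news in *at-or-below* is 16%, 35%, 50% and 62% at w = 0.25, 0.5, 0.75 and 1.

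**4. The arm that H5b splits.** Table 6 gives 287 informed and 1,306 controls for mean CVD risk. Check: (1.96 + 0.84)² = 7.849, unexplained variance 1 − 0.36 = 0.64, design effect 1 + 9 × 0.1 = 1.9.
- Control arm: 2 × 7.849 × 0.64 × 1.9 / (0.6 × 0.2)² = 1,326 (stated 1,306).
- Information arm: 7.849 × 0.64 × 1.9 / 0.04 = 238.6, and 1/(1/238.6 − 1/1,306) = 292 (stated 287).

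Both are within 3%, so the inputs are understood.

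**5. A split on both answers.** Suppose D moves towards C. If C > B then D ≥ U, so P > D implies P > U. If C ≤ B then D ≤ U, so P ≤ D implies P ≤ U. Groups with the same direction at both steps are therefore on the right side by construction; a simulation showing no errors adds no evidence. In the second model, respondents with bad news twice are 11–28% of the arm under overestimation, and those with good news twice can be as few as 6–8% under underestimation. At 6%, 11% and 28% of 287 (17, 32 and 80 people), the detectable effect is 2.80 × √[0.64 × (d/n + 1.9/1,306)]. With d between 1 (members thinly spread over barangays) and 1.9, this is 0.55–0.75, 0.41–0.55 and 0.26–0.36 SD, against 0.20 SD for the whole arm.

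**The case against.** The strongest reply is that the most worrying error needs the opposite of what the plan expects. A reader might infer that pure bias correction will routinely be reported as reduced ambiguity. The documents do not support that. [H2c] expects base rates to be overestimated. Then only 0–23% of the *at-or-below* group has net bad news in either model, and its mean belief falls by about 7 points or more, so correction alone would not imitate ambiguity. Imitation on average appears only with mean underestimation and w of about 0.75 or more. This stands.

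Nor can one say that the second worked case is common under [H2c]. That depends on w and on the scatter of beliefs, and the documents give neither.

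The plan also words its inference cautiously, adds a look at stated confidence, and compares D_T with D_C. These help, but the D_T versus D_C comparison shows only an average shift and re-sorts nobody. H5b is one mechanism hypothesis among many, and the principal outcome is untouched. That limits the importance of the point without removing it.

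Finally, splitting the controls by the same rule would not help: their section D answer precedes any information, while the information arm's follows the base rate.

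**Conclusion.** The mismatch between sorting and effect is in the text and needs no assumption beyond the one the plan itself tests, that base-rate information moves D. It follows that the plan's bias-only prediction is not valid for the groups as defined. The size of the damage cannot be known from the documents; every share above is conditional on assumed beliefs.

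Under [H2c] the main harm is to the *above* group. Respondents with net good news dilute it, and its mean belief change can reverse when the told base rate largely replaces the perceived one (in the first model, already at w = 0.5 if the overestimation averages 15 points). A false ambiguity result is possible but needs the less expected conditions described under the objection. The point calls for a change to a secondary analysis and its reading. It does not touch the design or the main comparison.

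**What to change.** Keep the planned two-indicator regression. Add a split based on two comparisons already available in the data: told base rate against the section B answer, and told personal risk against the section D answer.
- Bad news at both steps: rest the bias-correction reading here.
- Good or neutral news at both steps: rest the ambiguity reading here, and only if stated confidence, which the plan already examines, also rises in this group.
- Mixed: report without either reading.

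State that the section G message (reasons for excess risk and ways to lower it, Section 5.2) is another route to healthier behaviour, which this split does not remove. Nor does it change the comparison with an unsplit control group.

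The cost is wording and one extra regression, with no new data. The price is precision. Roughly 16–51% of the arm falls in the mixed group under the assumed beliefs, and the interpreted groups may number only a few dozen, so these contrasts should be labelled exploratory and shown with confidence intervals.
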